### 1041 **Follow-up of Adverse Events**

1042 During and following a subject's participation in a clinical trial, the sponsor-investigator  
1043 and institution will provide adequate medical care to the study subject for any study-  
1044 related adverse events, including clinically significant laboratory values related to the  
1045 study. This medical care for study subjects will be provided regardless of their insurance  
1046 status.

1047 All adverse events classified as serious or severe or possibly/probably related to the trial  
1048 product must be followed until the subject has recovered and all queries have been  
1049 resolved. For cases of chronic conditions follow-up until the outcome category is  
1050 “recovered” is not required, as these cases can be closed with an outcome of “recovering”  
1051 or “not recovered”.

1052 All other adverse events must be followed until the outcome of the event is “recovering”  
1053 (for chronic conditions), or “recovered” or until the end of study, whichever comes first,  
1054 and until all queries related to these AEs have been resolved.

1055

#### 1056 **Pregnancy**

1057 Study subjects will be instructed to notify the sponsor-investigator immediately if they  
1058 become pregnant. If using liraglutide this medication will be discontinued immediately.

1059

1060 The sponsor-investigator will report to Novo Nordisk any pregnancy occurring during the  
1061 trial period. Reporting of pregnancy by sponsor-investigator should occur within the  
1062 same timelines described above for reporting of Adverse Events.

1063

1064 Pregnancy complications will be recorded as adverse event(s). If the infant has a  
1065 congenital anomaly/birth defect this must be reported and followed up as a serious  
1066 adverse event.

1067

#### 1068 **Precautions/Over-dosage**

1069 The following precautions and procedures will be observed in the event of overdose by  
1070 any trial product provided during the study: if asymptomatic, the patient is instructed to  
1071 call the study doctor immediately after discovering the overdosage and obtain case-  
1072 specific instructions; if symptomatic, the patient is instructed to call the EMS for  
1073 immediate treatment.

1074

#### 1075 **LIABILITY AND SUBJECT INSURANCE:**

1076 During and following a subject’s participation in trial, the sponsor-investigator and  
1077 his/her institution will provide adequate medical care to the study subject for any study-  
1078 related adverse events, including clinically significant laboratory values related to the  
1079 study. This medical care for study subjects will be provided regardless of their insurance  
1080 status.

1081

1082 The sponsor-investigator will be responsible for the conduct of the study and that the  
1083 sponsor-investigator agrees to defend, indemnify, and hold harmless Novo Nordisk, any  
1084 of its parent companies, affiliates, or subsidiaries, and their respective officers, directors,  
1085 employees, agents, representatives, distributors, salespersons, customers, licensees, and  
1086 end-users from and against any claim, suit, demand, loss, damage, expense or liability  
1087 imposed by any third party arising from or related to: (a) any breach of sponsor-  
1088 investigator's obligations; or (b) sponsor-investigator’s negligent or grossly negligent use  
1089 or willful misuse of the study drug, the results, or services derived therefrom. This  
1090 indemnification shall not apply in the event and to the extent that a court of competent  
1091 jurisdiction or a duly appointed arbiter determines that such losses or liability arose as a

1092 result of Novo Nordisk's gross negligence, intentional misconduct, or material breach of  
1093 its responsibilities.

1094

1095 **EVALUABILITY OF SUBJECTS:**

1096 All patients and collected data will be included in the intention to treat analysis.

1097 A secondary confirmatory analysis will be performed using only completers data, where  
1098 all data from patients with an overall compliance rate during the study period of <50%  
1099 will be excluded. The subjects and observations to be excluded, and the reasons for their  
1100 exclusion will be documented and signed by those responsible prior to database release.  
1101 The documentation must be stored together with the remaining trial documentation.

1102

1103 **PREMATURE TERMINATION OF STUDY:**

1104 Study can be discontinued if funding is withdrawn or by the Data Safety Monitoring  
1105 Board (DSMB) if there is evidence of futility or excess harm. The study statistician will  
1106 monitor the data quarterly and discuss any observed trends with the other members of the  
1107 DSMB who will make such decision following pre-established guidelines.

1108

1109 **PUBLICATION PLAN:**

1110 We plan to publish the data from this clinical trial in peer reviewed scientific journals  
1111 (i.e. Diabetes Care). We anticipate at least two manuscripts to results from this work  
1112 (possibly one on clinical efficacy and safety, one on healthcare utilization and cost  
1113 data). We expect the final manuscripts to be completed around December 1st, 2016. All  
1114 manuscripts will be submitted to Novo Nordisk for review and commenting 1 month  
1115 before external submission. We also plan to present the data at the American Diabetes  
1116 Association and/or The Endocrine Society scientific meetings as poster or oral  
1117 presentations.

1118 We have registered the study with [clinicaltrials.gov](http://clinicaltrials.gov).

1119

1120  
1121  
1122  
1123  
1124  
1125  
1126  
1127  
1128  
1129  
1130  
1131  
1132  
1133  
1134  
1135  
1136  
1137  
1138  
1139  
1140  
1141  
1142  
1143  
1144  
1145  
1146  
1147  
1148  
1149  
1150  
1151  
1152  
1153  
1154  
1155  
1156  
1157  
1158  
1159  
1160  
1161  
1162  
1163  
1164

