**STATISTICAL CONSIDERATIONS:**

**Sample Size Calculation**

We propose to test a non-inferiority hypothesis comparing the 6-month change from baseline in HbA1c between the two treatment groups, with a non-inferiority margin of 0.4%. We conservatively estimate the standard deviation of the difference at 0.5% based on results from reported studies with similar design[44, 45, 47]. Using a one-sided alpha of 0.025, we determine that 44 subjects per group completing 6 months will provide power 0.96 to test this non-inferiority hypothesis, shown below amongst with other scenarios (Hintze, J. (2011). PASS 11. NCSS, LLC. Kaysville, Utah, USA. [www.ncss.com](http://www.ncss.com)). We will need to randomize 100 patients to test this hypothesis assuming a 12% drop-out rate (estimated drop-out rate based on our extensive prior experience with similar population and length of study). We plan to screen 120 patients to account for approximately 20% anticipated screen failures.

Power and sample size estimation for Non-Inferiority Test (H0: Diff >= NIM;  
H1: Diff < NIM)  
Higher Means are Worse  
Test Statistic: T-Test

Power	N1/N2	Non-Inferiority Margin (NIM)	Actual Difference (D)	Significance Level (Alpha)	Beta	Standard Deviation1 (SD1)
1.000	44/44	0.4	0	0.025	0.000	0.3
1.000	48/48	0.4	0	0.025	0.000	0.3
1.000	50/50	0.4	0	0.025	0.000	0.3
0.960	44/44	0.4	0	0.025	0.040	0.5
0.973	48/48	0.4	0	0.025	0.028	0.5
0.977	50/50	0.4	0	0.025	0.023	0.5
0.755	44/44	0.4	0	0.025	0.245	0.7
0.791	48/48	0.4	0	0.025	0.209	0.7
0.808	50/50	0.4	0	0.025	0.192	0.7

Further, this sample size will yield at least 80% power at two-sided alpha=0.05, superiority hypothesis, for the secondary composite outcome endpoint of HbA1c<7% with no hypoglycemia and no significant weight gain, expecting that 25% and 5% reach

726 this endpoint with liraglutide treatment and standard basal-bolus insulin treatment,  
727 respectively.

728

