### 735 **Statistical Analysis Plan**

736 All statistical analyses will be performed by the study statistician ([name]), who  
737 has extensive experience in clinical trials analysis.

738 Primary analysis: The primary analysis will be intention-to-treat (ITT) which will include  
739 all randomized participants who receive at least one dose of a study medication. The  
740 non-inferiority of liraglutide treatment strategy compared to standard basal-bolus insulin  
741 regimen will be assessed using a 95% confidence interval for the between treatment  
742 group net difference (month 6 minus month 0) in HbA1c at 6 months. This 95%  
743 confidence interval will be derived from the differences of least square means estimated  
744 from a mixed model repeated measures analysis. Non-inferiority of liraglutide treatment  
745 will be concluded if the upper limit of the 95% confidence interval is less than the non-  
746 inferiority margin of 0.4%.

747

748 Secondary analyses: We will also perform a per-protocol analysis comparing HbA1c  
749 response because, in non-inferiority hypothesis testing, the ITT analysis may be biased  
750 toward the null hypothesis. The per-protocol population is defined as the population who  
751 continued the assigned intervention as randomized for the duration of the study period.  
752 Secondary outcomes include the composite endpoint of HbA1c<7% with no  
753 hypoglycemia and no significant weight gain, a binary variable, which will be compared  
754 between the randomized study groups with a logistic regression model. The odds ratio  
755 and corresponding 95% confidence intervals will be reported. From healthcare related  
756 cost data, cost-effectiveness ratios will be summarized as point estimates with 95%  
757 confidence intervals, accounting for the skewness in the distribution of the ratio[50].  
758 Sensitivity cost analyses will be performed to further assess variables such as treatment  
759 failure and quality of life weights. Multiple logistic regression models will be constructed  
760 to evaluate any association of baseline covariates on treatment efficacy. Binary  
761 secondary endpoints will also be assessed with logistic regression models. Group  
762 comparisons and changes from baseline over time (study visits) of continuous secondary  
763 outcome variables will be analysed with mixed model repeated analysis. The logrank test  

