764 will be used to compare the pre-specified “treatment failure” end-point between groups.  
765 Safety endpoints and hypoglycemic and other adverse events will summarize in detail  
766 with descriptive statistics. The analysis of safety data will be performed for the ITT  
767 population.

768 Model assumptions regarding normality and covariance structure will be carefully  
769 assessed. Nonparametric tests or data transformations will be used if necessary to meet  
770 assumptions. Statistical analysis will be performed with SAS software (SAS Institute,  
771 Cary NC), particularly Proc Mixed for linear models with both fixed and random effects.

772 A two-sided alpha <5% will be considered significant for all analyses.

773

774 **Interim Analysis**

775 No interim analysis is planned.

776

777 **DATA HANDLING AND RECORD KEEPING:**

778 All data will be collected in strict compliance with the University's HIPPA rules.

779 Research records (source documents) will be kept in a double-locked filing system in a  
780 secure locked room. Collected data will be stored in an electronic study database will be  
781 encrypted and password protected and saved on the University's secure network. Only  
782 study personnel will have access to these records.

783

784 The institutional review board (IRB) governing this study may inspect the medical  
785 records of any patient involved in this study at any time.

786

787 Laboratory specimens will be collected under standard of care protocol at Parkland  
788 hospital laboratory and handled in accordance with the hospital policy.

789

790 The study blind will be maintained by the designated statistician and only broken by  
791 request from a treating physician in case of a medical emergency.

792

793 **ETHICS:**

794 Ethical Considerations:

795 1. Exclusion of non-English speakers- while translators are available during working  
796 hours, the investigators are worried that no translator will be available to assure  
797 safety measures at all times.

798 2. Compliance with Insulin Regimen- At times patients are not compliant with  
799 complicated insulin regimens and providers often continue to uptitrate insulin  
800 dosage when patients remain above HbA1c goal. If patient compliance improves  
801 once enrolled in the study, there is a higher risk of hypoglycemia. Every effort  
802 will be made at all visits to determine exactly what amount of insulin the patient  

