### 1018 **Data Safety Monitoring Board (DSMB)**

1019 An independent DSMB will be set up for the trial to oversee safety and perform ongoing  
1020 safety surveillance. The DSMB will be composed of 3 members who cover the relevant  
1021 specialty as well as an independent statistician:

- 1022 • [name] (Endocrinology)
- 1023 • [name] (Endocrinology)
- 1024 • [name] (Endocrinology)
- 1025 • [name] (Statistician)

1026 The first meeting will occur after the enrolment of 15 subjects or three months after the  
1027 first patient is enrolled, whichever comes first. The meetings will then occur on a  
1028 quarterly basis, although the board may request more frequent meetings as needed. A  
1029 formal report approved by all DSMB members will be sent to the PI and study  
1030 coordinator within 3 weeks of the meeting and then forwarded to the IRB.

1031

1032 All AEs will be presented at each meeting and will be available for informal review by  
1033 the DSMB at any time after study initiation. All SAE and unanticipated but related AE  
1034 will be promptly reported to the IRB (within 2 working days of PI's awareness for SAEs  
1035 and within 10 working days for other reportable AEs). We intend to comply with all  
1036 local legal, regulatory, and IRB requirements. We will also report to Novo Nordisk all  
1037 SAEs, SUSARs, and SADR at the same time such events are reported to regulatory  
1038 authorities or within 15 working days from the sponsor-investigator becoming aware of  
1039 such adverse events, whichever comes first.

1040

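### Interim analysis is ruled out, yet the DSMB may stop for futility on trends the study statistician reviews quarterly, with no rule given and that statistician's place on the board unclear

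*Combined protocol and SAP*

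**What the plan says.** The Interim Analysis section of the Statistical Analysis Plan consists of one statement: "No interim analysis is planned".

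Premature Termination of Study says that the trial can be discontinued by the Data Safety Monitoring "Board (DSMB) if there is evidence of futility or excess harm. The study statistician will" then "monitor the data quarterly and discuss any observed trends with the other members of the" DSMB. The sentence ends by saying that the board decides by guidelines set in advance. No endpoint, boundary, timing or binding status for those guidelines appears anywhere in the documents.

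The Data Safety Monitoring Board section gives a different picture: "An independent DSMB will be set up for the trial to oversee safety and perform ongoing" safety surveillance. It lists three endocrinologists and an independent statistician, with quarterly meetings, and does not mention futility.

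On the study statistician's other duties, the Randomization sections assign generation of the allocation scheme to that person, and the Statistical Analysis Plan says "All statistical analyses will be performed by the study statistician".

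The Sample Size Calculation is for a design without looks: "Using a one-sided alpha of 0.025, we determine that 44 subjects per group completing 6 months will provide power 0.96".

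**The concern.** Two separate matters need reconciling.

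**Whether there are interim looks.** To judge futility is to ask whether the trial can still reach its objective, here non-inferiority on HbA1c. That normally needs a comparative look at accumulating efficacy data. A plan cannot both exclude interim analysis and permit a futility stop without saying what the board looks at. If such stops are used, some trials that would have shown non-inferiority end early, and power can fall below the fixed-design value.

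**Who looks.** As worded, the study statistician takes part in quarterly discussion of trends as one of the board. The same person runs the final analysis, and several choices are left to that stage. Covariance structure, transformation and nonparametric alternatives depend on an assessment of assumptions. The supporting analysis set is defined in two ways: as patients who continued the assigned intervention (Statistical Analysis Plan), and as completers after exclusion of those with compliance below 50% (Evaluability of Subjects), with exclusions settled before database release. If by-arm trends are known before those choices are made, the choices are open to influence, or to the suspicion of it. In a non-inferiority trial the supporting analysis set carries real weight.

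**Working it through.** **1. Reproduce the plan's power.** Inputs from Sample Size Calculation: 44 completers per arm, margin 0.4, SD 0.5, true difference 0, one-sided alpha 0.025, two-sample t-test.

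- Standard error = 0.5 × √(2/44) = 0.1066.
- Noncentrality θ = 0.4 / 0.1066 = 3.752, with 86 degrees of freedom.
- Noncentral t power = 0.960. The normal approximation Φ(3.752 − 1.960) gives 0.9635.
- Randomised number: 88 / (1 − 0.12) = 100.

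The plan's figures reproduce. They describe one analysis at the end.

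**2. Timing of possible looks (assumption).** Study schedule gives 12 months of recruitment, and follow-up is 6 months. With uniform accrual, month-6 data arrive between months 6 and 18. Quarterly reviews at months 9, 12 and 15 would then see 25%, 50% and 75% of them. The plan sets quarterly monitoring; it does not set quarterly tests of month-6 HbA1c.

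**3. Candidate rules (assumption).** Let t be the fraction of information and B the score process with drift θ. Conditional power is Φ((B + d(1 − t) − 1.96) / √(1 − t)), where d = θ under the design assumption or d = B/t under the current trend.

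The first look shows how far these rules differ. At t = 0.25 there are about 11 patients per arm, and the standard error of the difference is 0.5 × √(2/11) = 0.213.

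- Current-trend conditional power below 20% means B/t < 1.960 − 0.842 × 0.866 = 1.231, so an observed difference above 0.4 − 1.231 × 0.1066 = 0.27. With no true difference this happens about 10% of the time (0.269 / 0.213 = 1.26 standard errors).
- Design-assumption conditional power below 20% means B < 1.960 − 0.75 × 3.752 − 0.729 = −1.583, so an observed difference above 0.4 + (1.583 / 0.25) × 0.1066 = 1.07. This almost never happens.

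**4. Simulated power.** 400,000 runs per scenario, normal approximation (no-look baseline 0.963), binding stops, SD 0.5, true difference 0, final critical value 1.96.

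| Assumed stopping rule, looks at 25%, 50%, 75% | Power |
|---|---|
| Design-assumption conditional power below 10% to 50% | 0.964 to 0.956 |
| Observed difference at or beyond the margin | 0.939 |
| Current-trend conditional power below 10% | 0.894 |
| Current-trend conditional power below 20% | 0.861 |
| Current-trend conditional power below 30% | 0.828 |
| Observed difference beyond half the margin | 0.78 |
| Current-trend conditional power below 50% | 0.764 |

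With a single look at 50%, the current-trend 20% rule gives 0.933. At SD 0.7, which is also in the plan's table, the three-look results run from 0.761 (design-assumption, 10%) to 0.487 (current-trend, 50%), against a no-look baseline of 0.765.

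**5. Type I error.** With the true difference set at the margin, the one-sided error stays near 0.025 under the lenient rules and falls to about 0.010 under the most aggressive one. Futility stopping alone does not inflate it.

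**The case against.** The best reply is that the documents do not show any loss. The board decides by guidelines set in advance, which may sit in a charter outside these documents. A lenient rule costs under one percentage point at SD 0.5. The larger losses in the table depend on binding stops and mostly on the very early look: under the current-trend 20% rule, dropping the 25% look raises power from 0.86 to 0.93. The text speaks of data and trends; it does not say by arm and does not name HbA1c. The wording that places the study statistician on the board could be a drafting slip, since the DSMB section already provides an independent statistician.

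All of this limits the point, and three stronger readings should be set aside.

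- A reader might infer that the 0.96 is wrong. It is right for its inputs. The documents support only that it is not shown to hold once futility stops are used.
- A reader might infer inflated type I error from repeated looks. The termination section names futility and harm, with no early stop for success, and step 5 shows no inflation.
- A reader might infer that the study statistician and the board's statistician are one person, so that independence is lost. Names are removed, and this cannot be checked.

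The contradiction remains. A charter with futility guidelines would itself conflict with the statement that no interim analysis is planned. If the two statisticians are different people, the study statistician is still worded as discussing trends with the board every quarter.

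**Conclusion.** The point holds as a contradiction to be reconciled. Interim Analysis, Data Safety Monitoring Board and Premature Termination of Study cannot all be followed as written, and no futility rule is given. The bias risk is conditional on the study statistician seeing by-arm trends, which the text permits but does not state; it is avoidable at almost no cost.

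The effect on power cannot be given as one number. It lies between about 0.96 and about 0.76 at SD 0.5, assuming true difference 0, 44 completers per arm, uniform accrual, three looks at month-6 data and binding stops. Fewer looks or non-binding use would reduce the loss; the plan's larger SD of 0.7 would increase it under most rules.

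**What to change.** Choose one version and make the three sections agree.

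- **Safety review only.** Remove futility from Premature Termination of Study, so that it matches Interim Analysis and the DSMB section. This keeps the 0.96. The price is the early futility stop, which is worth little here: on the assumed calendar the 50% look falls as recruitment closes and the 75% look after it.
- **Futility review kept.** Replace the Interim Analysis statement with the futility endpoint, the timing, a numeric boundary and its non-binding status, and restate the power under that rule.

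In either case, reword Premature Termination of Study so that the DSMB's independent statistician, already listed, prepares any by-arm reports and the study statistician sees only pooled data until database lock. Because the study statistician generates the allocation list, add that it is not linked to outcome data before lock. These are wording changes; they need no extra patients and no extra staff.
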